Risks and burdens added by the study	Risks due to the treatments D level
Number of participants included	50
Number of centres	5 ICUs in three different hospitals, national setting
Duration of the study	
 - inclusion period: 7 months - participation period (treatment + follow-up): 60days - total duration: 9 months
Number of enrolments expected per site and per month	1,4
Statistical analysis	Analysis will be made with an intent-to-treat design, without interim analysis. The primary endpoint, change of EVLWI from D1 to D7, will be compared between the two groups using analysis of covariance (ANCOVA). For patients dying before 7 days, the last thermodilution data will be retained for the primary analyses. If the patient's

	
condition no longer warrants the presence of the transpulmonary thermodilution systems, then the catheter is removed before 7 days. In this case, the measurement of EVLWi can no longer be made, the last thermodilution data will be retained for the primary analyses. A sensitivity excluding those patients will be performed for analysing the primary endpoint.

Funding sources	
 - MChE Handelsges m.b.H (F4-Pharma), Vienna, Austria, will provide the drug, and participates in the funding of the study - Bouygues SA - Sanofi SA 
None of the investigators has any conflict of interest with this study.

Study will have a Data Safety Monitoring Board	Yes

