4.2 Description of research methodology

4.2.1 Design of the study

Comparative, double-blinded, controlled (1:1), randomized trial, assessing the effect of FX06 infusion on the top of standard of care vs standard of care alone in 2 parallel arms, and multicentric (3 ICUs from three different hospitals).

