4.2.4 Randomisation

The randomization list will be computer-generated and stratified according to each ICU.

Patients will be randomly assigned in a 1:1 ratio to FX06 or standard of care.

Concealment of the study-group assignments is achieved with the use of a centralized, secure, interactive, Web-based response system (CleanWeb, Telemedicine Technologies) accessible from each study center.

After each randomization, a treatment number is allocated to the patient and a confirmation email of randomization is sent automatically to the investigator concerned and the URC.

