 - Positive end-expiratory pressure (PEEP)
 - Plateau pressure
 - FiO₂
 - Level of catecholamines: inotrope score, calculated as IS= dose of dubutamine (µg/kg/min)+ 100 x [dose of norepinephrine (µg/kg/min) + dose of epinephrine (µg/kg/min)] [16]
 - Supplementation by hydrocortisone Y/N
 - Biological exams :

- Arterial blood gases
 - Haematology (blood count)
 - Ionogram, renal and hepatic markers
 - serum glucose, CRP, LDH, NT-pro-BNP, procalcitonin, troponin
 - Coagulation tests: PT ratio, aPTT, Fibrinogenemia, D-Dimers
 - Albuminemia
 - ECG
 - SOFA score
 - RRT or not
 - Chest x-ray
 - Trans-thoracic echocardiography
- Assessment of transpulmonary thermodilution (TPT) parameters. **One measurement will be made before administration of the treatment [7]. All parameters will be evaluated in supine position. Parameters recorded will be: Extra-vascular lung water index, Global end-diastolic volume index, pulmonary vascular permeability index, and cardiac index.** Central venous and arterial lines used for the routine care of the patient will be compatible with TPT systems (either PICCO, Getinge, Germany or EV1000, Edwards Lifesciences, US).
- Treatment
 - Administration by IV perfusion 400mg FX06 intravenously or placebo as a two-time bolus within 10 minutes interval)
 - Administration as soon as possible after randomization, but no longer than 12 hours.
- Pharmacokinetic study: Additional 1 ml blood sample will be taken at time 0 (before FX06 application) and after 5, 15, 30, 60 min. Because FX06 in blood is quickly degraded by endopeptidases, the following sampling procedure should be followed: 1 ml blood to be collected into tubes containing Li-heparin, mixed by inversion 10 times, and then 0.8 ml of this blood to be transferred to test tubes containing 0.08 ml of 0.88 M HCl. It is critical that blood is being transferred to acid within 2 min of collection. The tubes are closed, the acidified blood samples will be mixed by inversion 10 times, and then processed to plasma by centrifugation (2500g; 10 min). Acidified plasma samples will be stored at a temperature of less than -20°C. FX06 dosage will be processed according by F4-Pharma, according to its dedicated procedure. Alternatively, pharmacokinetic study may be performed every other day of treatment (D1 to D5).

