12 STATISTICAL ASPECTS

12.1 Description of statistical methods to be used including the timetable for the planned interim analyses

The statistical analysis will be performed by a biostatistician of the Clinical Research Unit of Pitié-Salpêtrière Hospital, under the responsibility of [name] [name].

Statistical analyses will be performed with the SAS® or R software with the most recent version at the time of the analysis.

Descriptive analysis will always be overall and by treatment group.

Unless specially mentioned, comparative analysis between groups will be systematically performed without adjustment (univariate analysis);

Flow chart

A flow chart according to the CONSORT recommendations will describe the recruitment and the follow-up of all study population.

Study population

The primary analysis of efficacy endpoints will be performed on all randomized patients for whom a baseline evaluation is available, on an intention-to-treat (ITT) population. All patients will therefore be analyzed in their initial randomization groups.

The safety set is defined as all randomized patients having received at least one dose of study treatment. Safety endpoints will be analyzed on the safety set.

Descriptive analysis

Qualitative variables will be described with frequency and percentage distributions, and quantitative variables with median, interquartile range, minimum and maximum values, mean and standard deviation.

Censored data will be described by Kaplan-Meier estimation or cumulative incidence function, with rate at D7 and D30 with 95% confidence interval.

Baseline characteristics

Demographical, clinical, biological and treatment characteristics will be described.

Primary analysis

The primary analysis will be performed in the intention to treat population.

The primary outcome is the change in EVLWi between D1 and day 7. These changes will be compared between both arms using analysis of covariance (ANCOVA), adjusted for the D1 EVLWi. This is fully equivalent to comparing EVLWi scores at D7 adjusted for the baseline EVLWi. Results will be expressed in terms of adjusted mean changes, with their 95% confidence interval. The unadjusted supportive analysis will be carried out by comparing EVLWi at day 7 between the two arms with a t test.

If the distribution of EVLWi is clearly incompatible with the ANCOVA or t test assumptions, then these analyses will be conducted on the ranks.

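### Randomisation is stratified by ICU but the fixed primary ANCOVA omits ICU: if ICU predicts Day 7 EVLWi beyond baseline, the test is somewhat conservative and a few points of power are forgone (low severity)

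*Protocol*

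**What the plan says.** Protocol 4.2.4: "The randomization list will be computer-generated and stratified according to each ICU". The same section adds: "Patients will be randomly assigned in a 1:1 ratio to FX06 or standard of care". No other stratification factor is given there.

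Protocol 12.1, on the change in EVLWi from D1 to D7: "These changes will be compared between both arms using analysis of covariance (ANCOVA), adjusted for the D1 EVLWi". D1 EVLWi is the only covariate named.

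The general rule, also in 12.1, is: "Unless specially mentioned, comparative analysis between groups will be systematically performed without adjustment (univariate analysis". The secondary analyses in 12.1 (logrank, Fisher or chi-square, t or Wilcoxon, Poisson regression and linear mixed models) mention neither an ICU term nor stratification by ICU. The mixed model is there to handle within-subject correlation only.

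The number of strata is stated in two ways. Section 4.2.1, like the design row of the Summary, says "multicentric (3 ICUs from three different hospitals". The number-of-centres row of the Summary says "5 ICUs in three different hospitals, national setting", and the recruitment table in 6.3 also has 5 sites, with 10 subjects each.

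**The concern.** With 1:1 allocation balanced within each ICU, differences between ICUs largely cancel out of the treatment contrast. A model without ICU still counts those differences as residual noise. If ICU carries information about Day 7 EVLWi beyond the baseline value, the reported standard error exceeds the true sampling variability of the estimate. The interval is then wider than it need be, the test rejects less than 5% of the time under the null, and some power is given away.

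This is not a detail left to a later analysis plan. The protocol names the covariate and sets a no-adjustment default, so an analysis plan that added ICU would depart from the protocol. With 50 patients and no allowance for loss (12.5), efficiency that costs almost nothing is worth having.

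**Working it through.** **The plan's own figure.** Section 12.2 gives SD 5 ml/kg, baseline mean 13.4, a 30% decrease, 80% power and two-sided 5%.

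- Effect: 0.30 × 13.4 = 4.02 ml/kg.
- n per group = 2 × (1.96 + 0.84)² × 5² / 4.02² = 392 / 16.16 = 24.3, rounded up to 25. The stated 25 reproduces.
- Power at 25 per group is 81.1% by the normal approximation and 79.5% by the t distribution (which would need 26).

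**Inputs the protocol does not give (assumptions).**

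- Share *s* of the residual variance of Day 7 EVLWi (after baseline) that lies between ICUs: 0 to 0.30.
- Correlation ρ of D1 with D7 EVLWi: 0 and 0.5.
- Layout: 5 ICUs of 10 (the target in 6.3), with exact 1:1 balance within each ICU.

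**Why the standard error is too wide.** Let c = 5 × √(1 − ρ²) × √(2/25).

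- True sampling SD of the treatment estimate ≈ c × √(1 − s).
- Typical model SE without ICU ≈ c × √[(1 − s) + s × 40/47]. Here 40 = 10 × (5 − 1), from the between-ICU sum of squares, and 47 = 50 − 3 is the residual degrees of freedom.

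At ρ = 0, c = 1.414. For s = 0.20 the true SD is 1.414 × √0.80 = 1.265, and the model SE is 1.414 × √(0.80 + 0.170) = 1.393. The SE is therefore about 10% too large (1.393 / 1.265 = 1.10). Simulation under the null gave 1.29 and 1.40.

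**Simulation.** ANCOVA on baseline only against ANCOVA on baseline plus ICU, at 4.02 ml/kg, 8,000 trials per setting. Monte Carlo standard error is about √(0.8 × 0.2/8000) = 0.4 points for power and √(0.05 × 0.95/8000) = 0.2 points for type I error.

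| ρ | ICU share *s* | Type I error, without / with ICU | Power, without / with ICU |
|---|---|---|---|
| 0 | 0 | 4.9% / 5.1% | 79.1% / 78.9% |
| 0 | 0.10 | 4.4% / 5.3% | 79.9% / 82.1% |
| 0 | 0.20 | 3.5% / 4.9% | 81.9% / 86.9% |
| 0 | 0.30 | 2.9% / 5.0% | 84.4% / 90.9% |
| 0.5 | 0 | 5.2% / 5.2% | 88.5% / 88.6% |
| 0.5 | 0.10 | 4.4% / 5.4% | 90.1% / 91.4% |
| 0.5 | 0.20 | 3.6% / 5.2% | 91.5% / 94.3% |
| 0.5 | 0.30 | 2.6% / 5.1% | 93.1% / 96.7% |

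The power forgone runs from 2.2 to 6.5 points at ρ = 0 and from 1.3 to 3.6 points at ρ = 0.5.

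**Checks on the layout.** With 3 ICUs (16, 16 and 18 patients), s = 0.20 and ρ = 0, power is 82.6% without ICU and 86.6% with it. Permuted blocks of 4 within ICU, in place of exact balance, give a similar picture: type I error of about 4%, 4% and 2.7%, and gains of about 1–2, 3–5 and 4–7 points for s = 0.10, 0.20 and 0.30.

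**A persistent device offset.** Here an ICU-level offset is present at both D1 and D7, with ρ = 0.5 and 6,000 trials per setting. With the offset at 10, 20 and 30% of total variance, power without / with ICU is 91.9 / 91.9%, 93.9 / 94.3% and 95.8 / 96.4%. Type I error without ICU is 4.8, 4.6 and 5.0%. The gain is under 1 point.

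**The case against.** The strongest reply is that the harm is conditional. It needs ICU to predict Day 7 EVLWi after baseline adjustment, and the protocol gives no evidence of how far it does. For a share up to 0.10 the loss is about 0 to 2 points, and at zero there is nothing to gain. That stands, and it limits the point to low severity.

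A reader might take the choice of thermodilution systems in 5.1 ("compatible with TPT systems (either PICCO, Getinge, Germany or EV1000, Edwards Lifesciences, US") as proof that ICU matters. The documents do not support this. They do not say that the device differs by ICU. An offset that affects a patient's D1 and D7 readings alike is also largely removed by the D1 adjustment already planned, as the last check shows. A more relevant route is local practice after D1. For example, section 7.4 ties specific antiviral treatment to each hospital's written policy. That ICUs differ in this respect is inference.

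It can also be said that the no-adjustment rule is only a default, since it opens with an exception clause. That is correct. The rule need not be deleted, and a stated exception is enough. But no exception for ICU is stated now.

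Finally, neither the block size nor equal recruitment of 10 per ICU is guaranteed by the text. The 3-ICU and blocks-of-4 runs suggest that the result is not sensitive to either.

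**Conclusion.** The mismatch between design and analysis is real and is fixed in the protocol. Its consequence is a modest, conditional loss of efficiency. If ICU accounts for 10 to 30% of the residual variance, type I error falls from about 4% to about 2.7%. The power forgone at 4.02 ml/kg is then about 1 to 4 points at baseline correlation 0.5 and about 2 to 7 points at correlation 0. If ICU has no effect, or only a persistent offset that D1 largely absorbs at correlation 0.5, the difference is about 1 point or less either way. The ICU share and the correlation are both assumptions.

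Two stronger readings do not follow. The primary test is not invalid: any error is on the conservative side, with no inflation of type I error. Nor is the sample size wrong: 25 per group rests on the total SD, it reproduces, and power without ICU stays near or above 80% in every setting run.

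The conflict between 3 and 5 ICUs is a separate documentary contradiction. It is no evidence of an analysis error, but it leaves the strata undefined. Low severity.

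**What to change.** In 12.1, specify the primary model as *ANCOVA adjusted for D1 EVLWi and ICU (randomisation stratum)*. Add ICU to the linear mixed models for the longitudinal outcomes, worded as a stated exception to the no-adjustment default. The default can otherwise stay.

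The cost is a sentence or two of text and 2 degrees of freedom with 3 ICUs or 4 with 5 (47 falls to 43 in the primary model). If ICU turns out not to be prognostic, the price is under 1 point of power.

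Separately, state one number of ICUs in both rows of the Summary, in 4.2.1 and in 6.3, and make the stratified randomisation list match it.

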As per article R.1123-49 of the *Code de la Santé Publique (French Public Health Code)*, the investigator notifies the sponsor without delay (and at the latest within 24 hours) on the day the investigator becomes aware of any serious adverse event which occurs during a study that meets the description in line 1° of Article L.1121-1 of the Code de la Santé Publique, with the exception of any event which is listed in the protocol and, if applicable, in the investigator’s brochure as not requiring notification.

A serious adverse event is any untoward medical occurrence that:

- 1- results in death
- 2- is life-threatening to the participant enrolled in the study
- 3- requires hospitalisation or prolongation of existing hospitalisation
- 4- results in persistent or significant disability/incapacity

It should be noted that the sponsor will particularly monitor the frequency of deaths occurring during the first 5 days (it concerns less than 25 % of the deaths in a prospective cohort of 36 patients meeting criteria for inclusion (18)).

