For patients dying before 7 days, the last thermodilution data will be retained for the primary analyses. If the patient's condition no longer warrants the presence of the transpulmonary thermodilution systems, then the catheter is removed before 7 days. In this case, the measurement of EVLWi can no longer be made, the last thermodilution data will be retained for the primary analyses. A sensitivity excluding those patients will be performed for analysing the primary endpoint.

Secondary analyses

For safety, the types and severity of AEs and SAEs will be described as frequency and percent by treatment arm. Fisher's exact tests will be used to compare the two treatment arms in terms of proportion of patients with death (all cause), at least one AE/SAE, at least one SAE. The number of these events (except death) will be compared between arms by Poisson regression.

Overall survival at D30 will be compared between the two groups using a logrank test.

The evolution of EVLWi during 7 days and other longitudinal repeated efficacy secondary outcomes will be compared between the two groups using a linear mixed effect model to take into account within subject correlation. If the model assumptions (normally distributed residuals with constant variance) is debatable, these analyses will be conducted on the ranks.

For other efficacy secondary outcomes, data will be described graphically and compared between arms by:

- chi2 test or fisher test for binary outcomes;
t-test or wilcoxon rank-sum test for quantitative variables.

Subgroups analyses will be performed according to :

- Presence of VV-ECMO at baseline (Yes/No)
- EVLWi at baseline (>10 ml/kg) (Yes/ No)

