12.2 Calculation hypotheses for the number of participants required and the result

According to previous studies, standard deviation for EVLWi during ARDS is around 5 ml/kg predicted body weight [2]. Assuming a baseline mean of EVLWi of 13.4 and a 30% decrease in EVLWi in FX06 treated patients compared to controls at Day 7, **for 80% power and an overall 5% two-sided α -risk**, the required sample size is **25 patients per group**.

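### One carry-forward rule for the primary EVLWi endpoint covers both early death and catheter removal, and the sensitivity analysis that drops those patients does not test it

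*Protocol*

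**What the plan says.** Protocol section 12.1 (Primary analysis) defines the endpoint: "The primary outcome is the change in EVLWi between D1 and day 7". It is analysed by ANCOVA adjusted for the D1 value. Two situations without a D7 reading are then given the same treatment; the summary's statistical paragraph says the same.

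- Death: "For patients dying before 7 days, the last thermodilution data will be retained for the primary analyses".
- Catheter removal: "If the patient's condition no longer warrants the presence of the transpulmonary thermodilution systems, then the catheter is removed before 7 days". In that case "the measurement of EVLWi can no longer be made, the last thermodilution data will be retained for the primary analyses".

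The sensitivity analysis follows directly: "A sensitivity excluding those patients will be performed for analysing the primary endpoint".

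Section 12.1 also plans a linear mixed model on EVLWi over the 7 days. It is listed with the secondary analyses and not as a check on the primary result. Ranks are used only if distributional assumptions fail, and nothing says that a death would rank worst.

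**The concern.** Death and removal on improvement are opposite outcomes, and carrying the last value forward distorts each in its own way.

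- **Death.** The D1 reading is taken before treatment (section 5.1) and the D2 reading at 10 o'clock on D2 (section 5.2.1). A patient who dies between them contributes a change of exactly 0, a better score than that of a survivor whose EVLWi rises. A patient who dies later contributes a value from before the final deterioration.
- **Removal.** A patient who improves enough to lose the catheter is frozen at that day's value, and any later change is lost.

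The exclusion analysis does not show whether this matters. It keeps only patients who survived and still needed the catheter, and treatment may affect both conditions. It swaps one untested assumption for another. If death or removal differs by arm, the protocol offers no designated analysis that shows how far the primary estimate depends on the rule.

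**Working it through.** **Inputs from the protocol**
- "standard deviation for EVLWi during ARDS is around 5 ml/kg predicted body weight" (section 12.2).
- "Assuming a baseline mean of EVLWi of 13.4 and a 30% decrease in EVLWi in FX06 treated patients compared to controls at Day 7" (section 12.2), so the planned difference is 0.30 × 13.4 = 4.02 ml/kg.
- 25 per group, 80% power, two-sided 5% (section 12.2).
- Mortality around 60% (section 2.4).
- On deaths in the first 5 days: "it concerns less than 25 % of the deaths in a prospective cohort of 36 patients meeting criteria for inclusion" (section 10.3.2.1).

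**The plan's own figure.** n = 2 × (1.960 + 0.842)² × 5² / 4.02² = 24.3, rounded up to 25 per group. It reproduces. It makes no allowance for missing D7 values.

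**How many patients may die early.** 0.60 × 0.25 = 0.15, and 0.15 × 50 = 7.5 patients. This is an upper bound through D5 and combines two sources. Deaths between D5 and the D7 reading would add to it, as would removals, for which no rate is given.

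**Scenario A, early deaths differ by arm (all rates and trajectories assumed).** Early death is 30% on FX06 and 10% on control. In both arms survivors fall by 2 ml/kg by D7, and dying patients rise by 1 ml/kg per day. Differences are FX06 minus control.
- If every patient's D7 value were available, dying patients would be at +6 and survivors at −2, a gap of 8. The arm difference is 0.20 × 8 = 1.6 ml/kg.
- With last readings spread over D1 to D4, dying patients carry +1.5 on average, a gap of 3.5. The arm difference is 0.20 × 3.5 = 0.7 ml/kg.
- After exclusion only survivors remain, with the same trajectory in both arms, so the difference is 0. This follows from the assumption.

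**Scenario B, equal rates in both arms (assumed).** In each arm 15% die, carrying 25% of the effect, and 15% have the catheter removed, carrying 60% of it. The true effect is 4.02 ml/kg.
- Effect under carry-forward: 4.02 × (0.70 + 0.15 × 0.25 + 0.15 × 0.60) = 4.02 × 0.8275 = 3.33 ml/kg.
- Simulated ANCOVA power (25 per arm, D1–D7 correlation 0.5) falls from about 89% without the events to about 83% with linear trajectories. With autoregressive trajectories it is about 79%.
- The events here fall at random, so exclusion would return close to 4.02 with fewer patients. Exclusion works only under that condition.

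**Scenario C, events tied to trajectory (assumed).**
- Removals placed in the best trajectories, 10% on control and 30% on FX06: a true reduction of 4.02 is estimated as 3.10 under carry-forward and 2.91 after exclusion.
- Early deaths placed in the worst trajectories, 15% on control and 35% on FX06, with no effect on EVLWi: the estimates are −0.46 and −1.17 ml/kg. Both favour FX06, the opposite sign from Scenario A.

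If both events are equally frequent in the two arms and unrelated to treatment, and there is no treatment effect, the estimate is essentially unbiased.

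**The case against.** The strongest reply is that EVLWi is a mechanistic endpoint in a phase IIa trial, and that mortality is examined in its own right. That is correct. A reader might infer that the plan could hide a harmful drug; the protocol does not support this. Section 12.1 gives Kaplan-Meier or cumulative-incidence rates at D7 and D30 by arm, a Fisher test on all-cause death and a log-rank test at D30. Sections 6.3 and 10.3.4 pause inclusion for DSMB review, including deaths in the first five days, and section 10.3.2.1 has the sponsor watch those deaths. These looks are weak at 25 per arm: Fisher power is about 30% for 10% v 30% and 25% for 15% v 35%. But they exist. Scenario A would also usually be missed with complete data, since power for 1.6 ml/kg is only 20% to 25%.

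A reader might also put 3.33 ml/kg into the power formula with the SD unchanged and report 76% (or 64% unadjusted). That overstates the loss. Carried-forward values lie closer to baseline, so the ANCOVA residual SD falls too, and the unadjusted test is only supportive.

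Finally, the mixed model on daily EVLWi is already planned, and an SAP not shown here may add sensitivity analyses. Both points limit the finding. They do not remove it, because the protocol itself fixes the carry-forward rule and names the exclusion as its check.

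**Conclusion.** The point holds for interpretation of the primary endpoint, not for the trial's ability to see deaths. One rule is applied to two opposite events, and the sensitivity analysis named for it cannot reveal the consequences when treatment affects survival or the need for the catheter. Up to about 15% of patients may be affected through death by D5, plus an unknown share through removal.

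The illustrations (1.6 seen as 0.7 or 0; 4.02 seen as about 3.3, with power from about 89% to about 83%) rest on assumed rates and trajectories. They show a range and are not a forecast; even the sign of the bias changes between scenarios. The sample size calculation is not in error on its own assumptions. This should be fixed before analysis, but it does not invalidate the design.

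**What to change.** Keep the primary analysis. Replace or supplement the exclusion analysis in section 12.1 with two named sensitivity analyses:

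- **(a)** The D7 treatment contrast from the planned D1–D7 mixed model, fitted to observed EVLWi with nothing carried forward. It addresses catheter removal.
- **(b)** A rank analysis adjusted for D1 EVLWi in which death before D7 ranks below every survivor. It addresses death.

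Report the carried-forward patients by arm, reason (death or removal) and last day measured.

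The cost is protocol or SAP wording and two model runs on data already collected daily, with two more estimates to report. Analysis (a) assumes data are missing at random and implicitly extrapolates EVLWi after death. Analysis (b) is a composite that mixes mortality with EVLWi. Agreement in direction between them should not become a pass/fail rule for robustness: with about seven early deaths, a chance imbalance could reverse (b).

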- The mortality of those severe forms of the disease is very high, around 60% [3], justifying an urgent research to find an appropriate treatment.
 - The level of vascular leak is an independent predictor of mortality during ARDS.
-

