10.3.2.2 Specific features of the protocol

10.3.2.2.1 Other events that require the investigator to notify without delay the sponsor

- Adverse events judged as being "medically significant" not listed in the normal and natural course of the condition (see below)
 - Major bleeding (bleeding necessitating a transfusion of more than 4 packed red blood cells), in the absence of invasive procedure
 - Anaphylactic shock at the time of drug injection
 - Clinical worsening: rescue with VV-ECMO

The investigator must notify the sponsor **without delay (and at the latest within 24 hours) on the day when the investigator becomes aware** of these adverse events, according to the same modalities and within the same timeline as for serious adverse events (see above).

- **In utero exposure**

The investigator must notify the sponsor without delay on the day the investigator becomes aware of any pregnancy that occurs during the study, even if it is not associated with an adverse event.

If the investigational medicinal product is genotoxic, every case of maternal or paternal exposure must be notified.

Notify using a specific form appended to the protocol.

- **Exposure while breastfeeding**

Exposure while breastfeeding occurs if an infant or a child may have been exposed to a medicinal product via the breast milk of a mother being treated with an investigational medicinal product.

Even if it is not associated with an adverse event, the investigator must notify the sponsor without delay on the day the investigator becomes aware of the exposure while breastfeeding.

10.3.2.2.2 Serious adverse events that do not require the investigator to notify the sponsor without delay

These serious adverse events are simply recorded in the case report form. A CRF extraction of these serious adverse events will be realized according to Data Safety Monitoring Board (DSMB) or AP-HP's Safety department's request.

- **Normal and natural course of the condition:**

SARS-CoV-2 induced ARDS is an extremely severe condition, with up to 60% ICU mortality [3]. Moreover, the condition, consisting in severe hypoxia, may affect all organs.

Serious adverse events linked with the condition include particularly:

- Hemodynamic worsening
 - Liver cytolysis/insufficiency
 - Acute renal failure
 - Diffuse intra-vascular coagulation/bleedings
 - Leucopenia/thrombopenia/anemia
 - Severe mesenteric ischemia
 - Brain death/hemorrhagic stroke/ischemic stroke
 - Pulmonary embolism
-

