12.3 Anticipated level of statistical significance

Analyses will be performed with a two-sided alpha risk of 5%.

12.4 Statistical criteria for termination of the study.

No interim analysis will be performed.

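### The Poisson comparison of adverse-event counts states no allowance for overdispersion or unequal time at risk, so its model-based p-values would be too small in this population

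*Protocol*

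**What the plan says.** Section 12.1, under secondary analyses, describes adverse events and serious adverse events by arm. It compares the proportions of patients who died, had at least one AE/SAE, or had at least one SAE by Fisher's exact test. For counts it then states: "The number of these events (except death) will be compared between arms by Poisson regression". Nothing is said about time at risk, the variance estimator, a check for overdispersion or a fallback. The same section makes between-group comparisons unadjusted unless stated otherwise, and section 12.3 sets a two-sided 5% level.

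Other outcomes get more. Repeated efficacy measures have a "linear mixed effect model to take into account within subject correlation", and both they and the primary ANCOVA have a rank-based fallback.

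Four other statements bear on the count model:
- Section 2.4 puts mortality at around 60%, and section 10.3.2.2.2 at up to 60% in the ICU.
- Section 10.3.2.2.2 adds: "Moreover, the condition, consisting in severe hypoxia, may affect all organs". It lists renal, hepatic, coagulation, cardiac, neurological and infectious events as part of the natural course.
- The schedule in section 5.6 marks adverse events up to Day 30 and not at Day 60. Section 5.4 collects serious adverse events at Day 60.
- Section 12.5 expects no loss to follow-up, so death is the main reason why time at risk differs.

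**The concern.** Model-based Poisson inference takes the variance of a patient's count to equal its mean. Two features of this trial push the variance above the mean. Patients who die early have little time in which to have events, and failure of several organs can give some patients many events and others few. Standard errors are then too small and p-values too optimistic.

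A second, separate effect is on the estimate. Without an exposure term, an arm that lives longer collects more events at the same daily rate. Improved 30-day mortality is a stated secondary hypothesis (section 3.2). If it were true, the raw count could count against FX06 for that reason alone. Tolerance is also a stated objective, so the count comparison will be read.

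**Working it through.** **The plan's own figure.** The only design figure is the sample size in section 12.2. With a difference of 0.30 × 13.4 = 4.02 and SD 5, n = 2 × (1.960 + 0.842)² × 5² / 4.02² = 24.3, so 25 per group. It reproduces. The protocol gives no event rate, dispersion or power for safety.

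**Inputs from the protocol.** 25 per arm; two-sided 5%; 60% mortality, here placed at Day 30.

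**Assumed inputs.** Exponential deaths; 2, 4 or 6 events per 30 patient-days; a gamma patient effect with variance k = 0 (no clustering) or 0.5 (moderate). The exponential choice puts (1 − 0.4^(5/30)) / 0.6 = 23.6% of the deaths by Day 30 in the first 5 days, in line with the figure of less than 25% in section 10.3.2.1.

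**Step 1: time at risk.** Hazard λ = −ln(0.4)/30 = 0.0305 per day. Over 30 days the mean time at risk is E(T) = 0.6/λ = 19.6 days. With E(T²) = 500.6, the variance is 500.6 − 19.64² = 114.7.

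**Step 2: variance/mean ratio of the counts.** For daily rate r, φ = 1 + r × [(1 + k)E(T²) − E(T)²] / E(T). With k = 0 and r = 4/30, φ = 1 + 0.1333 × 114.7/19.64 = 1.78.

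**Step 3: false-positive rate at nominal 5%.** 2 × [1 − Φ(1.96/√φ)]. Simulations of 20,000 trials per scenario, with no difference in event rate, are beside it.

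| Events per 30 patient-days | k | φ | Formula | Simulated |
|---|---|---|---|---|
| 2 | 0 | 1.39 | 9.6% | 9.7% |
| 4 | 0 | 1.78 | 14.2% | 14.0% |
| 6 | 0 | 2.17 | 18.3% | 18.4% |
| 2 | 0.5 | 2.24 | 19.0% | 18.0% |
| 4 | 0.5 | 3.48 | 29.3% | 29.2% |
| 6 | 0.5 | 4.72 | 36.7% | 36.5% |

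If instead 4 events per patient are confined to the first 7 days, E(T) = 6.30 and the variance of T is 2.83. Then φ = 1 + (4/7) × 2.83/6.30 = 1.26, and the rate is about 8% with k = 0 (about 27% with k = 0.5).

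**Step 4: what repairs the error rate.** In the six scenarios of the table, an offset alone gives about 5% at k = 0 but 14 to 29% at k = 0.5. Robust variance alone gives about 4 to 6%, and offset plus robust variance about 5 to 7%. The variance estimator does most of the repair.

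**Step 5: unequal survival.** Assume 40% v 60% mortality at Day 30 and equal daily event rates.

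| Period in which events accrue | Mean days at risk | Ratio without offset |
|---|---|---|
| 30 days | 23.5 v 19.6 | 1.20 |
| 60 days | 37.6 v 27.5 | 1.37 |
| First 7 days only | 6.60 v 6.30 | 1.05 |

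**Step 6: an offset over the wrong window.** If events fall only in the first 7 days but the offset runs to death or end of follow-up, the ratio becomes 1.05/1.20 = 0.87 over 30 days and 1.05/1.37 = 0.77 over 60 days. The longer-surviving arm would look falsely safe.

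**The case against.** The strongest reply is that much of this rests on silence. Poisson regression can carry an offset, a scale parameter or a sandwich variance, and an offset is compatible with an unadjusted comparison. A statistical analysis plan that is not shown may fix these details. That stands as far as it goes: a reader might infer that the model definitely has no offset and uses model-based variance, and the protocol does not say so. It does name a specific model whose basic variance assumption conflicts with the mortality and organ involvement that it expects. It also gives its other models a remedy for failed assumptions and gives this one none. Replacing the named method is therefore more than supplying a missing detail.

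Two stronger readings are tempting and are not supported.
- *The safety analysis as a whole has too many false positives.* Only the count comparison has the variance problem. The Fisher tests do not, although the proportions with at least one event also ignore time at risk. The safety reviews after 10 and 30 patients (section 6.3) rest on extractions of mortality, serious events, clinical worsening and laboratory tests, with no stated rule tied to a Poisson p-value.
- *FX06 will look less safe because its patients live longer.* This needs a survival difference, which is only a hypothesis of unstated size, and events spread over follow-up. Halving a death hazard of 0.03 per day gives 39.6/27.8 = 1.42 over 60 days. Adverse events are scheduled only to Day 30, where the same hazards give 24.2/19.8 = 1.22. With events in the first week, plausible given five days of dosing in acutely ill patients, little of the effect remains.

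**Conclusion.** The point holds in a limited form. If the Poisson model is fitted with its model-based variance and no exposure term, the nominal 5% test has a true error rate of about 10 to 18% from unequal survival alone, more if events cluster, and about 8% if events are early and unclustered. These figures rest on assumed event rates, assumed dispersion and exponential deaths; the protocol supplies only the mortality, the sample size and the alpha. The distortion of the estimate is conditional: about 1.2 over 30 days for an assumed 40% v 60% mortality with events accruing throughout, and about 1.05 with early events. Nor would an offset always remove it fully. In a simulation where the same frailty (k = 0.5) drove both events and death, the ratio over 30 days was 1.34 without an offset and still 1.09 with one.

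One secondary safety comparison is affected. The primary endpoint and the stated decision rules are not.

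**What to change.** Replace the sentence on Poisson regression with text to this effect: numbers of AEs and SAEs (except death) will be compared by negative binomial regression, or by Poisson regression with robust (sandwich) or quasi-likelihood variance. Rate ratios with 95% confidence intervals will use log(days at risk) as offset, with time at risk counted from first dose to death or the end of the window, whichever comes first. The windows will be an early one around treatment (for example D1–D7), Day 30 for AEs and Day 60 for SAEs. The analysis without offset will be shown alongside.

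Showing both versions matters because an offset over full follow-up overcorrects when events are early. An offset alone is not enough, because it leaves clustering untouched. Keep the Fisher tests.

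The change takes a few lines and no new data collection, since vital status and the date of death are already recorded. The cost is wider intervals by a factor of √φ: about 22% at variance/mean 1.5, 41% at 2 and 73% at 3. That width reflects the true uncertainty. With 25 per arm the corrected tests are close to nominal but not exact (about 5 to 7% in the simulations of offset plus robust variance).
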